10.5.2.4 Other safety data

ECG

- The number (%) of patients with notable values will be presented; also, data on ECG results will be listed for all patients with at least one abnormality.

Vital signs

- Data on vital signs will be tabulated and listed, notable values will be flagged. The number (%) of patients with notable values will be presented.

Physical examination

- Shift table baseline to worst on-treatment result
- Table with descriptive statistics at baseline, one or several post-baseline time points and change from baseline to this/these post-baseline time points.

10.5.2.5 Supportive analyses for secondary objectives

Additional supportive analysis may be conducted if appropriate.

10.5.2.6 Tolerability

Not applicable

10.5.3 Pharmacokinetics

Not applicable

10.7 Sample size calculation

The primary objective is to evaluate the efficacy of eltrombopag on overall hematopoietic response (partial or complete) by 16 weeks in patients with PGF after receiving an allo-HSCT. When the sample size is 33 patients and the proportion of responses with eltrombopag is assumed to be 45% in this sample, a one-sided 95% CI of such proportion will have a length of 0.149 towards its lower end. In other words, this CI will provide enough evidence that the actual proportion of responses in the target population is above 30%, because its lower limit (as per the sampling distribution) would be 30.1.

Table 10-1 Sample size justification

Confidence level	Minimally acceptable response	Distance of observed response to lower limit	Observed proportion	Actual lower limit	Sample size
95%	>30%	14.9%	45%	30.1%	33

The calculation of the sample size has been performed using the exact method described by Clopper and Pearson (*Newcombe RG. Two-sided confidence intervals for the single proportion: comparison of seven methods. Stat Med 1998; 17:857-72*) as implemented in the version 15 of the PASS software (NCSS statistical software: PASS version 15, available at: ncss.com/software/pass).

Statistical Methodology:

As mentioned, a one-sided confidence interval will be constructed for the proportion of responders using the formula indicated on [Section 10.4.2](#).

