Rationale of the sample size	
The primary objective is to evaluate the efficacy of eltrombopag on overall hematologic response (partial and complete) in patients with PGF after receiving an allo-HSCT. When the sample size is 33 patients and the proportion of responses with eltrombopag is assumed to be 45% in this sample, a one-sided 95% confidence interval of this proportion will have a length of 0.149 towards its lower end. In other words, this confidence interval will provide enough evidence that the actual proportion of responses in the target population is above 30%, because its lower limit (as per the sampling distribution) would be 30.1%.
 
  
 Confidence level	Minimally acceptable response	Distance of observed response to lower limit	Observed proportion	Actual lower limit	Sample size	
   
 95%	>30%	14.9%	45%	30.1%	33	
  
 
The calculation of the sample size has been performed using the exact method described by Clopper and Pearson (Newcombe RG. Two-sided confidence intervals for the single proportion: comparison of seven methods. Stat Med 1998; 17:857-72) as implemented in the version 15 of the PASS software (NCSS statistical software: PASS version 15, available at: ncss.com/software/pass).
	Confidence level	Minimally acceptable response	Distance of observed response to lower limit	Observed proportion	Actual lower limit	Sample size	95%	>30%	14.9%	45%	30.1%	33
Confidence level	Minimally acceptable response	Distance of observed response to lower limit	Observed proportion	Actual lower limit	Sample size								
95%	>30%	14.9%	45%	30.1%	33								
Data analysis	
A one-sided confidence interval will be constructed for the primary efficacy endpoint (proportion of responders by 16 weeks after the initiation of eltrombopag) using the relationship between the sums of binomial probabilities and the F distribution described by Clopper and Pearson using the formulas proposed elsewhere (Fleiss JL, Levin B, Paik MC. Statistical Methods for Rates and Proportions. Third edition. John Wiley & Sons: New York, 2003, pp. 25):
 $P_L = \frac{x_0}{x_0 + (n - x_0 + 1)F_{2(n-x_0+1), 2x_0; \alpha}}$ 
Where $\alpha=0.05$, x_0 is the observed number of responders in the sample and n the sample size.
												

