10.4.2 Statistical hypothesis, model, and method of analysis

No hypotheses or models will be considered for these analyses and descriptive statistics will be provided; inferences to the target population (when applicable) will be made using interval estimation.

The proportion of patients who reach the overall response rate (partial and complete) by 16 weeks after the initiation of eltrombopag will be calculated and the corresponding 95% confidence interval (CI). This CI will be one-sided and will be constructed using the relationship between the sums of binomial probabilities and the F distribution described by Clopper and Pearson using the formulas proposed elsewhere (Fleiss JL, Levin B, Paik MC. Statistical Methods for Rates and Proportions. Third edition. John Wiley & Sons: New York, 2003, pp. 25):

$$P_L = \frac{x_0}{x_0 + (n - x_0 + 1)F_{2(n-x_0+1), 2x_0; \alpha}}$$

where $\alpha=0.05$, x_0 is the observed number of responders in the sample and n the sample size.

Descriptive statistics will also be provided between baseline and 16 weeks for blood cell counts (ANC and platelet) and hemoglobin levels, and appropriate paired exploratory tests will be done according to the type of distribution (parametric or not) to assess the statistical significance of the changes.

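### The case for 33 patients treats the assumed 45% response rate as the result: the lower limit exceeds 30% only with at least 15 responders, which has a probability of about 55% if the true rate is 45%

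*Protocol*

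**What the plan says.** Protocol section 10.7 starts from a stipulated result: "When the sample size is 33 patients and the proportion of responses with eltrombopag is assumed to be 45% in this sample". From that, "a one-sided 95% CI of such proportion will have a length of 0.149 towards its lower end". It then concludes that "this CI will provide enough evidence that the actual proportion of responses in the target population is above 30" per cent, "because its lower limit (as per the sampling distribution) would be 30.1" per cent. The protocol summary, under the rationale of the sample size, says the same: "this confidence interval will provide enough evidence that the actual proportion of responses in the target population is above 30" per cent.

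Table 10-1 sets this out in one row: a minimally acceptable response above 30%, an observed proportion of 45%, a lower limit of 30.1%, a distance of 14.9% and a sample size of 33. On method: "The calculation of the sample size has been performed using the exact method described by Clopper and Pearson".

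Section 10.4.2 describes the primary analysis as estimation: "No hypotheses or models will be considered for these analyses". It specifies the one-sided exact interval with alpha 0.05, computed from the observed number of responders.

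Neither document gives a power, a probability that the limit will exceed 30%, or the number of responders needed. The SAP has no sample size section.

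**The concern.** The passage moves from an assumption to a conclusion. The 45% is a planning value: section 2.2 takes the response-rate hypothesis from studies in refractory severe aplastic anemia, and section 1.2.1.2 cites 44% in a 25-patient phase II study. Section 10.7 and Table 10-1 enter that value as the observed proportion and then say what the interval will show. Nothing allows for the sample rate falling below the assumed rate, which happens about half the time when the assumption is right.

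This is the only justification given for 33 patients. A reader or an ethics committee would conclude that 33 patients are enough to show a rate above 30% if eltrombopag works as assumed. The gap would also matter afterwards. A result of 14 of 33 is quite compatible with a true 45%, yet its lower limit is below 30%, and nothing written in advance would tell readers how likely that was.

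**Working it through.** **Inputs.** n = 33, assumed rate 45%, reference rate 30%, one-sided 95% (section 10.7 and Table 10-1); alpha = 0.05 and the exact formula (section 10.4.2).

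**Formula.** The lower limit in section 10.4.2 equals the 5% quantile of a Beta(x, n − x + 1) distribution, where x is the number of responders.

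**Step 1: reproduce the plan's figure.** 0.45 × 33 = 14.85 responders. The 5% quantile of Beta(14.85, 19.15) is 0.3008, and 0.45 − 0.3008 = 0.149. Both stated figures are reproduced. On this calculation 33 is the smallest n that clears 30%: n = 32 (14.4 responders) gives 0.2985. The size was therefore set where the assumed result only just passes.

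**Step 2: use whole patients.**

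| Responders of 33 | Rate | One-sided exact 95% lower limit |
|---|---|---|
| 14 | 42.4% | 27.8% |
| 15 | 45.5% | 30.5% |
| 16 | 48.5% | 33.3% |

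The limit exceeds 30% with 15 or more responders and not with 14. At 15 of 33 the distance is 45.45 − 30.49 = 14.96, or 15.0 points.

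**Step 3: probability of at least 15 responders.** This is the binomial tail P(X ≥ 15) for X ~ Bin(33, p).

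| True rate p | P(lower limit > 30%) |
|---|---|
| 30% | 4.4% |
| 40% | 31.9% |
| 44% | 50.0% |
| 45% | 54.6% |
| 50% | 75.7% |
| 55% | 89.9% |
| 60% | 96.9% |

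At the plan's own 45%, the chance of not exceeding 30% is 1 − 0.546 = 0.454.

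**Step 4: dependence on n.** Under the same rule, the count needed is 14 at n = 30, 15 at n = 32 or 33, and 16 at n = 34 or 35. The protocol summary plans approximately 33 patients and the primary analysis uses the FAS, so the count of 15 is tied to exactly 33 analysed.

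**The case against.** The best defence is that section 10.7 is a precision statement. It is conditional on 45% in the sample, and under that condition it is right: every attainable result at or above 45% clears 30%, and the failing result, 14 of 33, lies below 45%. The plan disclaims hypotheses, section 2.2 calls the design a pilot, and no decision is tied to 30%. All of this stands. A reader might infer an arithmetic error from the 14.85 responders, but the documents do not support that: 30.1% follows from the stated method, and rounding up to 15 gives 30.5%. The fractional count is secondary. It matters only because it hides that one responder decides which side of 30% the limit falls on.

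It is also fair to say that the 55% belongs to a true rate of 45%. Section 1.2.1.2 reports 8 responders in a series of 12 patients with poor graft function, 9 of them without GVHD. Even at a true 8/12 (66.7%), the probability is above 99%. That series is small and its response definition is not given, and section 2.2 names the aplastic anemia studies as the basis of the hypothesis. So 45% is the fair planning value, but a range should be shown.

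The defence does not cover the last step. The text goes beyond a width: it sets a minimally acceptable rate and says that the interval will show the true rate to be above it. A purely descriptive plan gives no support for that promise.

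**Conclusion.** The sample-size justification is overstated, although its arithmetic is correct. The interval shows a rate above 30% only if at least 15 of 33 patients respond. At the plan's own 45%, the probability of that is 54.6%, and it ranges from 32% at a true 40% to 97% at 60%. These figures assume 33 patients in the FAS, independent responses with a common rate, and the one-sided interval of Protocol section 10.4.2. SAP section 10 says only that 95% intervals will be shown. If they were two-sided, 15 of 33 would give 28.1%, 16 responders would be needed, and the probability at 45% would be 40.8%.

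A reader might go further and infer that the trial misses its power, or that 33 patients are too few. Under the same rule, 80% at a true 45% is first reached at n = 67. The documents do not support that criticism: they state no power, set no target and test no hypothesis. Sizing on precision is legitimate. The analysis and the reported interval are not affected. What needs correcting is the claim about what 33 patients can show.

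**What to change.** Keep 33 patients, the endpoint, the interval and the estimation framework. In Protocol section 10.7 and the protocol summary:

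1. Replace the promise of sufficient evidence with a statement conditional on the count, for example: *If at least 15 of 33 patients respond (45.5%), the lower limit of the one-sided exact 95% CI exceeds 30% (30.5% at 15 of 33); with 14 of 33 (42.4%) it is 27.8%. If the true response rate is 45%, at least 15 responders occur with probability of about 55% (32% at 40%, 76% at 50%, 90% at 55%, 97% at 60%).*
2. In Table 10-1 and its copy in the summary, replace the 45% and 30.1% row with 15/33 = 45.5%, lower limit 30.5%, distance 15.0 points.
3. Add that the count applies to exactly 33 analysed patients and will be recalculated if the FAS differs (for example 14 at n = 30, 16 at n = 34 or 35).

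The cost is a change of wording in two places and a less favourable stated figure. No patients are added and no analysis changes.

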10.8 Power for analysis of key secondary variables

Not applicable.

11 Ethical considerations and administrative procedures

11.1 Regulatory and ethical compliance

This clinical study was designed, shall be implemented and reported in accordance with the ICH Harmonized Tripartite Guidelines for Good Clinical Practice, with applicable local regulations (including European Directive 2001/20/EC and US Code of Federal Regulations Title 21), and with the ethical principles laid down in the Declaration of Helsinki.

11.2 Responsibilities of the investigator and IRB/IEC/REB

The protocol and the proposed informed consent form must be reviewed and approved by a properly constituted Institutional Review Board/Independent Ethics Committee/Research Ethics Board (IRB/IEC/REB) before study start. Prior to study start, the investigator is required to sign a protocol signature page confirming his/her agreement to conduct the study in accordance with these documents and all of the instructions and procedures found in this protocol and to give access to all relevant data and records to Novartis monitors, auditors,

Novartis Clinical Quality Assurance representatives, designated agents of Novartis, IRBs/IECs/REBs and regulatory authorities as required.

11.3 Informed consent procedures

Eligible patients may only be included in the study after providing written (witnessed, where required by law or regulation) IRB/IEC/REB-approved informed consent or, if incapable of doing so, after such consent has been provided by a legally acceptable representative of the patient. In cases where the patient's representative gives consent, the patient should be informed about the study to the extent possible given his/her understanding. If the patient is capable of doing so, he/she should indicate assent by personally signing and dating the written informed consent document or a separate assent form.

Informed consent must be obtained before conducting any study-specific procedures (i.e. all of the procedures described in the protocol). The process of obtaining informed consent should be documented in the patient source documents. The date when a subject's Informed Consent was obtained will be captured in their CRFs.

Novartis will provide to investigators, in a separate document, a proposed informed consent form (ICF) that is considered appropriate for this study and complies with the ICH GCP guideline and regulatory requirements. Any changes to this ICF suggested by the investigator must be agreed to by Novartis before submission to the IRB/IEC/REB, and a copy of the approved version must be provided to the Novartis monitor after IRB/IEC/REB approval.

Women of child bearing potential should be informed that taking the study medication may involve unknown risks to the fetus if pregnancy were to occur during the study and agree that to participate in the study they must adhere to the contraception requirement for the duration of the study. If there is any question that the patient will not reliably comply, they should not be entered in the study.

Additional consent form

Not applicable

11.4 Discontinuation of the study

Novartis reserves the right to discontinue this study under the conditions specified in the clinical study agreement. Specific conditions for terminating the study are outlined in [Section 4.4](#).

11.5 Publication of study protocol and results

Novartis assures that the key design elements of this protocol will be posted in a publicly accessible database such as clinicaltrials.gov. Also, upon study completion and finalization of the study report the results of this study will be either submitted for publication and/or posted in a publicly accessible database of clinical study results.

11.6 Study documentation, record keeping and retention of documents

Each participating site will maintain appropriate medical and research records for this trial, in compliance with Section 4.9 of the ICH E6 GCP, and regulatory and institutional requirements

for the protection of confidentiality of subjects. As part of participating in a Novartis-sponsored study, each site will permit authorized representatives of the sponsor(s) and regulatory agencies to examine (and when required by applicable law, to copy) clinical records for quality assurance reviews, audits and evaluation of the study safety and progress.

Source data are all information, original records of clinical findings, observations, or other activities in a clinical trial necessary for the reconstruction and evaluation of the trial. Examples of these original documents and data records include, but are not limited to, hospital records, clinical and office charts, laboratory notes, memoranda, subjects' diaries or evaluation checklists, pharmacy dispensing records, recorded data from automated instruments, copies or transcriptions certified after verification as being accurate and complete, microfiches, photographic negatives, microfilm or magnetic media, x-rays, and subject files and records kept at the pharmacy, at the laboratories, and medico-technical departments involved in the clinical trial.

Data collection is the responsibility of the clinical trial staff at the site under the supervision of the site Principal Investigator. The study case report form (CRF) is the primary data collection instrument for the study. The investigator should ensure the accuracy, completeness, legibility, and timeliness of the data reported in the CRFs and all other required reports. Data reported on the CRF, that are derived from source documents, should be consistent with the source documents or the discrepancies should be explained. All data requested on the CRF must be recorded. Any missing data must be explained. Any change or correction to a paper CRF should be dated, initialed, and explained (if necessary) and should not obscure the original entry. For electronic CRFs an audit trail will be maintained by the system. The investigator should retain records of the changes and corrections to paper CRFs.

The investigator/institution should maintain the trial documents as specified in Essential Documents for the Conduct of a Clinical Trial (ICH E6 Section 8) and as required by applicable regulations and/or guidelines. The investigator/institution should take measures to prevent accidental or premature destruction of these documents.

Essential documents (written and electronic) should be retained for not less than fifteen (15) years from the completion of the Clinical Trial unless Sponsor provides written permission to dispose of them or, requires their retention for an additional period because of applicable laws, regulations and guidelines.

11.7 Confidentiality of study documents and patient records

The investigator must ensure anonymity of the patients; patients must not be identified by names in any documents submitted to Novartis. Signed informed consent forms and patient enrollment log must be kept strictly confidential to enable patient identification at the site.

11.8 Audits and inspections

Source data/documents must be available to inspections by Novartis or designee or Health Authorities.

11.9 Financial disclosures

Financial disclosures should be provided by study personnel who are directly involved in the treatment or evaluation of patients at the site - prior to study start.

12 Protocol adherence

Investigators ascertain they will apply due diligence to avoid protocol deviations. Under no circumstances should the investigator contact Novartis or its agents, if any, monitoring the study to request approval of a protocol deviation, as no authorized deviations are permitted. If the investigator feels a protocol deviation would improve the conduct of the study this must be considered a protocol amendment, and unless such an amendment is agreed upon by Novartis and approved by the IRB/IEC/REB it cannot be implemented. All significant protocol deviations will be recorded and reported in the CSR.

**LIST OF ABBREVIATIONS**

Abbreviation	Explanation
AE	Adverse Event
AESI	Adverse Event of Special Interest
ANC	Absolute Neutrophil Count
CI	Confidence Interval
EPO	Erythropoietin
G-CSF	Granulocyte Colony Stimulating Factor
KM	Kaplan-Meier
OS	Overall Survival
Q1	First quartile
Q3	Third quartile
PT	Preferred Term
SD	Standard Desviation
SOC	System Organ Class

## 1 INTRODUCTION

The analysis plan proposed below details the necessary aspects to know about the study and the statistical methods to be used to apply them in the final statistical analysis.

## 2 STUDY OBJECTIVES AND DESIGN

[figure not shown]
### 2.1 Study Objectives

#### Primary objective

To evaluate the efficacy of eltrombopag for poor graft function on overall hematologic response (partial and complete) as determined by platelets, hemoglobin and neutrophil counts, by 16 weeks after the initiation of eltrombopag.

#### Secondary objectives

1. To determine the response in each hematological lineage separately.
2. To evaluate the long-term efficacy of eltrombopag on overall hematologic response (partial and complete) at 24 and 36 weeks after the initiation of eltrombopag.
3. To evaluate the transfusion independence for red blood cells (RBC) and/or platelets after the initiation of eltrombopag.
4. To evaluate the reduction and discontinuation of concomitant granulocyte colony-stimulating factor (G-CSF) and/or erythropoietin (EPO) therapy.
5. To evaluate the overall survival and survival rate at 24 and 36 weeks.
6. To evaluate the safety of eltrombopag.

## 2.2 Study Design

This study is designed as an open-label, single-arm phase II study, in which patients diagnosed with primary or secondary PGF after allo-HSCT will be treated with eltrombopag up to week 36 or until the patient's premature withdrawal. If patient terminates eltrombopag for any of the reasons established in the withdrawal criteria, he/she will be followed for safety up to 30 days after the last dose of eltrombopag, unless he/she withdraws the consent, dies or is lost-to follow-up.

The primary efficacy endpoint is the overall hematologic response rate (partial and complete) by 16 weeks after the initiation of eltrombopag. Eltrombopag will be initiated on day 1 at a dose of 150 mg once daily (75 mg daily in Asian ancestry patients) and will be continued up to 36 weeks.

The study will consist of the following periods:

- Screening Period (baseline): the patient will be invited to participate in the study, after being informed of its characteristics. The patient screening criteria will then be reviewed, and the procedures established in the evaluation schedule will be performed.
- Treatment Period: from administration of the first dose of eltrombopag until time when patient permanently stops taking study treatment for any reason or until 36 weeks have passed.
  - Only patients with a partial or complete response at week 16 will continue to receive eltrombopag until loss of response (defined as a decrease in blood counts to levels that do not continue to meet the criteria for response established in this protocol), unacceptable toxicity, or discontinuation for any other reason.
  - Patients who discontinue eltrombopag because efficacy, will continue in the study and attend the scheduled visits of Treatment Period as per protocol. If loss of response occurs, eltrombopag will be reintroduced at the last effective dose.
- During the Treatment Period, patients will be evaluated weekly during the first month, every 2 weeks during the next 2 months and subsequently every 4 weeks until week 24. For the last 3 months, patients will be followed every 6 weeks.
- Final Visit (or Early Withdrawal): this visit will take place 30 days after completion of the Treatment Period, or premature patient withdrawal.

- Follow-up for Survival: all patients who discontinue from the study, regardless the reason of discontinuation, will be followed for survival for 24 and 36 weeks, unless they withdraw their consent, die or are lost-to follow-up, in which case will be censored at the last contact/follow-up, and study visits will no longer be carried out.

At 36 weeks of the study, the suitability of continuing with eltrombopag will be evaluated by the investigator, and the supply of the drug will be only commercial. Novartis will not supply eltrombopag after the end of the study.

The number of patients planned to be enrolled for the study is 33.

